Research Evaluating Sleep & Trends for Universal Prevention (REST-UP)

NCT04783519

03/27/2024

Statistical Design and Power

Preliminary analysis. Prior to inferential statistics, univariate and bivariate descriptive statistics will be used to assess distributions and simple relations among variables. Preliminary analyses will include nature of missing data, identification of extreme values and variable distributions. To establish randomization effectiveness, baseline equivalence on drinking measures and demographic representation will be examined between conditions. Preliminary efficacy (Aim 1) will be evaluated with respect to drinking behavior (quantity/frequency/peak drinking, total drinks per week, alcohol consequences) and sleep symptoms (as measured by the ISI and Promis). Secondary outcomes include MJ use and consequences.

To examine intervention differences in outcomes from post-intervention through 3-month follow-up, multilevel regression analyses (Gelman & Hill, 2007) – often referred to as Hierarchical Linear Modeling (HLM; Raudenbush & Bryk, 2002) or mixed-effects modeling (Pinheiro & Bates, 2000) – will be used. HLM has a number of advantages over traditional analytic techniques, such as repeated measures ANOVA, in that it allows for missing data, handles varying time-points, accommodates both time-varying and time-invariant covariates, and allows for flexible modeling of the correlation among repeated-measures. In the proposed project, each participant will provide up to 2 repeated measures (post-intervention, 3 months), yielding up to 300 Level 1 cases (repeated-measures) across 150 Level 2 cases (people). The following model will be the basis for analyses of specific aims:

$$\text{Level 1: } DV_{ti} = \pi_{0i} + \pi_{1i}(Time)_{ti} + \varepsilon_{ti} \quad \varepsilon_{ti} \sim N(0, I\sigma^2_{\varepsilon}) \quad (\text{Equation 1})$$

$$\begin{aligned} \text{Level 2: } \pi_{0i} &= \beta_{00} + \beta_{01}(DV_{pre})_i + \beta_{02}(Tx)_i + r_{00i} \\ \pi_{1i} &= \beta_{10} + \beta_{11}(DV_{pre})_i + \beta_{12}(Tx)_i + r_{10i} \end{aligned}$$

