where t indexes repeated-measures and i indexes participants. DV_{ti} represents the outcome vector for each individual from post-intervention through 3-months. $Time_{ti}$ measures weeks since end of intervention. DV_{pre} is the pre-intervention value of the outcome. (Note that sometimes DV_{pre} is included as the first datum in the outcome vector; most biostatisticians now reserve the outcome in treatment studies for post-randomization data that can be influenced by the treatment, see Harrell, 2004). Tx represents contrasts (i.e., dummy codes) for treatment condition. The multilevel model fits subject-specific effects via the random-effects (rs in Level 2); these “shrinkage” (Empirical Bayes) estimators are weighted combinations of individual and group level information. The model assumes independence of Level 1 residuals conditional on random-effects, and homoskedasticity and (multivariate) normality of Level 1 residuals and Level 2 random-effects (Atkins, 2005). The model depicted above represents the primary model to test intervention differences in outcome. The necessity of terms in the model will be assessed via Wald statistics for fixed-effects and deviance tests for random-effects. Clinical trials of psychological outcomes assessed repeatedly often have a nonlinear trajectory, which is well-modeled by the natural logarithm of time. If there is a nonlinear trajectory that is not fit via the log transformation, polynomials or spline fits will be used to model the curvature. Alcohol and MJ outcomes are frequently positively skewed, calling into question the use of the Normal distribution as the probability model. Rate and frequency variables, such as number of alcohol problems, often have skewed distributions that are better represented by the Poisson or Negative Binomial distributions (Atkins et al., 2013; Atkins & Gallop, 2007). Depending on observed outcome distributions, a generalized mixed-effects model with log-link a Poisson distribution may be appropriate (Raudenbush & Bryk, 2002). This model is a type of HLM with a Poisson distributed Level 1 outcome, the only notable change to equation 1.

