Aim 1b: Preliminary Treatment Outcome. The primary comparison is post-intervention differences between the BASICS + SLEEP vs. AOC and BASICS vs. AOC. The coding for Tx will depend on which hypothesis is being tested. Coefficients representing the main effect of treatment (i.e., “intercept” differences at post- intervention) and cross-level interactions of treatment contrast and Time will be used to test H1b. These two sets of coefficients will show whether there are treatment differences at the end of therapy and also across the 3-months post-therapy. As noted, appropriate Level 1 distribution (i.e., Normal or Poisson) will be used, determined by empirical distribution of outcomes. Secondary analyses will examine MJ using these approaches. We anticipate small-to-moderate effect sizes for alcohol and MJ use and moderate-to-large effects on sleep symptoms; recent trials have demonstrated large pre-post effects on alcohol and sleep indices for an integrated intervention with college students (Fucito et al., 2017).

Missing data. Multilevel models can incorporate missing data; however, validity of the findings depends on the missingness mechanism (see Atkins, 2005). There are 3 common assumptions for missing data (Schafer & Graham, 2002), and multilevel models provide unbiased results unless data are found to be non-ignorable (NI). HLM is generally resilient to missing data because HLM weights each person's final within-person slope and intercept estimates by the reliability of these estimates, which is influenced by the relative variance components and the number of observations that person provides. Data from individuals with fewer assessment points have less influence on the final results. More problematic is NI data, which arises when missingness depends on unobserved values of the outcome or upon a covariate not included in the model. In the present study, participants could fail to provide data due to alcohol use, which would yield NI missing data. This would only lead to NI data if the missingness were not related to earlier values of the DV.

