To deal with this possibility, we will use both design and statistical controls. First, as noted in Approach and Recruitment and Retention Plan in the Human Subjects and Clinical Trials section, we make every attempt to retain all participants at all assessments, and HLM models include all participants in all analyses even if missing data at some assessment points and/or on some items. Second, handling NI missing data is an active area of statistical research, and there are several options that attempt to provide unbiased estimates in the presence of NI missing data, including selection models, pattern-mixture models, and shared parameter models (Schafer & Graham, 2002). We will use the pattern-mixture approach to missing data that has been extended to HLM (Hedeker & Gibbons, 1997) to examine the sensitivity of our primary findings to key patterns of missing data. Should these sensitivity analyses reveal that the findings are dependent on missing data, the pattern-mixture approach will allow us to combine effects across missing data patterns to yield unbiased treatment results (see Hedeker & Gibbons, 1997 and Atkins, 2005 for examples).

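### With two outcome visits, the pattern-mixture analysis cannot deliver the unbiased 3-month effect that the SAP promises; it rests on an identifying restriction that the SAP does not state

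*SAP*

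**What the plan says.** The SAP (Preliminary analysis) sets the data for Equation 1: "each participant will provide up to 2 repeated measures (post-intervention, 3 months), yielding up to 300 Level 1 cases". Baseline enters as the covariate DV_pre and not as a third outcome. Under Aim 1b, "The primary comparison is post-intervention differences" of each active arm against AOC; in addition, "cross-level interactions of treatment contrast and Time will be used to test H1b". H1b in the protocol's Specific Aims covers both post-intervention and 3 months.

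Under Missing data, the SAP notes that "participants could fail to provide data due to alcohol use, which would yield NI missing data", and then limits this to missingness unrelated to earlier values of the outcome. Its analytic answer is a pattern-mixture model "to examine the sensitivity of our primary findings to key patterns of missing data". It goes one step further: "Should these sensitivity analyses reveal that the findings are dependent on missing data", then "the pattern-mixture approach will allow us to combine effects across missing data patterns to yield unbiased treatment results". The patterns are not defined. No identifying restriction, range of shifts or criterion for moving to the combined result is given.

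Equation 1 has a random intercept, a random slope on weeks and a single residual variance. The SAP assumes "homoskedasticity and (multivariate) normality of Level 1 residuals and Level 2 random-effects", does not state the intercept-slope covariance, and judges the need for random effects by deviance tests.

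**The concern.** A pattern-mixture model estimates the outcome within each dropout pattern and averages over patterns. With two visits, the pattern that matters most at 3 months is the group seen only at post-intervention, and nobody in that group has a 3-month value. Averaging then mixes an estimate from completers with an assumption about dropouts. Calling the result unbiased offers protection that the design cannot give, and the SAP allows that result to serve as the corrected treatment effect. At stake is the 3-month part of H1b.

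The random slope has a related problem. Two observations per person are asked to support more variance parameters than they can separate, and a deviance test is then asked whether the slope is needed.

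**Working it through.** **The plan's own figure.** Two visits, 50 per arm and ICC .6 give 2 x 50 x 2 = 200 observations and an effective size of 200 / (1 + .6) = 125, as the SAP's Power section states. The same two-visit, 50-per-arm, .6 and .5 SD inputs are used below.

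**Is the 3-month effect in post-only dropouts estimable?** Equation 1 has 8 fixed effects: intercept, DV_pre and two Tx dummies, each also multiplied by Time. There are two patterns, completers (both visits) and post-only dropouts (one visit).
- Pattern crossed with all terms: 16 columns, rank 12. The four terms that multiply pattern by Time are not estimable.
- Pattern on the intercept-level terms only: 12 columns, rank 12. This runs, but it assumes that dropouts change as completers do. It uses only the dropouts' post values, so it can neither detect nor correct a shift that appears only at 3 months.

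**Size of the 3-month bias.** Assumed: true effect -.50 when there is no shift; post-only share q = .10-.20 (from the 80-90% retention of earlier studies in the protocol's Preliminary/Pilot Studies, with all loss taken as post-only, so an upper bound for this pattern); dropouts in one active arm shifted by d = .25-.5 SD at 3 months only. Bias = q x d.
- Low end: .10 x .25 = .025, so the true effect is -.475.
- High end: .20 x .5 = .10, so the true effect is -.40.

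The ignorable model and the intercept-only pattern-mixture model both return about -.50. If q x d is the same in both arms, the bias in the contrast is zero.

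**Shift at which the conclusion changes.** Let b be the correlation of DV_pre with each outcome, v = 1 - b^2 and r = (.6 - b^2)/v. With the same q in both arms, SE^2 = (2/50) x v x [r^2 + (1 - r^2)/(1 - q)]. The tipping shift (two-sided .05) is (.50 - 1.96 x SE)/q. The SAP gives no value for b; 0 (no baseline adjustment) and .6 (the ICC carried over to baseline) are assumptions.

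| q | b | SE | Tipping shift (SD) |
|---|---|---|---|
| .10 | 0 | .207 | .94 |
| .20 | 0 | .215 | .39 |
| .10 | .6 | .167 | 1.72 |
| .20 | .6 | .176 | .77 |

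At q = .20, an effect of -.40 has p = .063 with b = 0 and p = .023 with b = .6. It falls below .05 from b of about .35 (p = .049; at b = .30, p = .053). The largest bias, .10 SD, is .10/.215 = .46 SE with b = 0 and .10/.176 = .57 SE with b = .6.

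**Can the combined result be worse than the main model?** This is an illustration only, because the SAP names no test for the switch. Let dropout depend on the observed post value, in AOC only, at log-odds 1 per SD. That is ignorable, and the main model returns -.50. By numerical integration the dropouts' post mean is .82 SD (q = .10) or .69 SD (q = .20) above the arm mean, so the completers' mean is -.091 or -.173. The intercept-only combination adds the completers' change, (.6 - 1) x (-.091) = .036 or (.6 - 1) x (-.173) = .069, to the AOC 3-month mean. The combined effect is then about -.54 or -.57 against a true -.50.

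**Random slope (Normal outcomes).** At weeks 0 and 13 (13 weeks taken for 3 months) there are 4 variance parameters and 3 moments. For any residual variance s, set intercept variance 1 - s, covariance (s - .4)/13 and slope variance 2(.4 - s)/169. Both visit variances are then 1 and the correlation is .6. Values s = .40, .30, .20, .10 and .05 all give this same matrix with a valid random-effects covariance. The data cannot choose between no slope variance (s = .40) and a large one (s = .05). If visit weeks vary between participants, the parameters are formally but weakly identified: with a true 13-week slope variance of .16, N = 150 and visit-time SD of 1 week (assumed), its standard error is .62. With the covariance fixed at zero, there are 3 parameters for 3 moments.

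**The case against.** The strongest reply is that little is at risk. The primary contrast is at post-intervention, where post-only dropouts are observed. The trial is a pilot reporting preliminary efficacy. The bias is modest even under arranged conditions: all loss after the post visit, a shift in one arm, and no trace of it at post-intervention. All of this stands and limits the size of the point. It does not rescue the word *unbiased*, because the 3-month effect is a stated part of H1b.

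Four stronger readings are tempting and are not supported.
- *The SAP expects non-ignorable dropout.* It says that this could happen and then narrows the circumstances.
- *The gap would overturn a significant 3-month result.* The move from p = .020 to p = .063 at 20% loss arises only if DV_pre is left out, and Equation 1 includes it. With a baseline correlation of about .35 or more, -.40 stays below .05.
- *The switch would misfire at a known rate.* Any such rate describes a test that the reader has supplied; the SAP names none.
- *The slope variance problem biases the efficacy estimates.* It does not. The three marginal covariance terms remain estimable, and the Tx and Tx x Time estimates are unaffected.

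**Conclusion.** The promise is wrong as written for the 3-month effect and should be corrected. With two outcome visits, any combined 3-month estimate is valid only under a restriction on unobserved change, and the SAP states none. Under the assumed 10-20% post-only loss and a .25-.5 SD shift in one arm, the bias is .025-.10 SD, at most roughly half a standard error, and zero when shift and dropout match across arms. The tipping shift at 20% loss is about .39 SD without DV_pre and .77 SD if baseline correlates .6 with the outcomes. A reader might infer that the main efficacy result is compromised; the documents do not support that, since the post-intervention contrast does not depend on the missing 3-month values.

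The random-slope point is secondary and minor. It holds exactly for Normal outcomes at common visit weeks with a free intercept-slope covariance, and as weak identification if weeks vary. Its consequence is that, under these conditions, the deviance test cannot show whether a random slope is needed.

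**What to change.** In the SAP's Missing data section:
- Name the dropout patterns and the identifying restriction for missing 3-month values, or use delta-adjusted multiple imputation.
- Apply it over a range of arm-specific 3-month shifts chosen by the sponsor, and report the shift at which the conclusion changes.
- Report it as sensitivity analysis only, and delete the move to the combined result.
- Replace *unbiased* with *valid under the stated restriction*.

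For Normal outcomes, drop the random slope and its deviance test and use an unstructured 2 x 2 within-person covariance. The fixed effects may keep weeks or use visit as a category.

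The cost is SAP wording and modest programming; no new data are needed. At common visit weeks with complete data, the SE of each contrast is sqrt(2/50) = .200 under either covariance model, without baseline adjustment. If visit is made categorical, small deviations in visit week are no longer modelled, and the post contrast is read at the mean visit week. For example, with post visits spread over weeks 0-2 (mean week 1) and an effect fading by .2 SD over 13 weeks, it would be -.50 + .2/13 = -.485. Keeping weeks in the fixed effects avoids this.

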Power. We used PASS software to estimate effect sizes based on proposed study sample size for Aim 1b. In Aim 1b, the models will be run such that there will be two repeated measures of the outcome at follow- up. Given 50 participants per condition, this means that there will be up to 200 observations for any one comparison of an intervention to the control group (2 conditions x 50 subjects per condition x 2 observations per subject). However, the effective sample size will be smaller than 200 due to the design effect for the correlation of observations within participants (Snijders & Bosker, 1999). Thus, we can use an effective sample size to estimate the effect of an intervention compared to control at any given follow-up visit. Given the sample size, 2 repeated observations, and an anticipated intra-class correlation (ICC) among survey responses for the same individual of .6, the effective sample size for any given comparison between two groups would be 125. Using this effective sample size and standardizing the sleep outcome with a mean of 0 and SD of 1, we would expect $>.8$ power to detect moderate-sized coefficients for the difference between intervention and control as small as .5. If the outcome were typical number of drinks per week, which tends to show a count distribution, and the base-rate were 4 drinks per week, then we expect $>.8$ power to detect a 32% increase in the count of drinks per week in the control compared to intervention group at any given follow-up (Rate Ratio = 1.32).

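### The effective N of 125 belongs to a two-visit average, not to a single visit: the sleep power (>.8 for .5 SD) is unsupported as derived, though not shown false for the planned baseline-adjusted model

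*SAP*

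**What the plan says.** The Power section of the SAP used PASS to "estimate effect sizes based on proposed study sample size for Aim 1b", so the sample size came first and the effects were worked back from it. It counts 2 conditions x 50 people x 2 observations = 200 for a pairwise comparison. With an "anticipated intra-class correlation (ICC) among survey responses for the same individual of .6", it concludes that "the effective sample size for any given comparison between two groups would be 125". The use it gives this number is: "Thus, we can use an effective sample size to estimate the effect of an intervention compared to control at any given follow-up visit". With the sleep outcome standardised to SD 1, it then claims more than .8 "power to detect moderate-sized coefficients for the difference between intervention and control as small as .5". For drinks per week it claims the same power for a rate ratio of 1.32 at a base rate of 4, again at any single follow-up.

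The SAP section on Aim 1b defines the target: "The primary comparison is post-intervention differences between the BASICS + SLEEP vs. AOC and BASICS vs. AOC". That difference is the treatment coefficient at the intercept; beside it, the "cross-level interactions of treatment contrast and Time will be used to test H1b". The model in the SAP's opening section (Equation 1) also adjusts for DV_pre, which "is the pre-intervention value of the outcome". The Power section gives no alpha, sidedness, pre-post correlation or number expected to be observed.

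**The concern.** An effective sample size larger than the number of people present cannot describe a comparison made at one visit. At one follow-up, a pairwise comparison has at most 50 + 50 = 100 participants, so a figure of 125 must draw on the other visit as well. The Power section and the Aim 1b section then describe different quantities: the first has the precision of a two-visit average, the second names a single-visit difference as primary.

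This paragraph is the SAP's only statement of what the pilot can detect. If the post-intervention sleep result is not significant, it will be read against .5 SD with more than .8 power, a benchmark derived for another contrast.

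**Working it through.** **Inputs.** From the SAP: 50 per arm, two follow-up visits, ICC .6, SD 1, sleep effect .5 SD, rate ratio 1.32 with base rate 4. Assumed because not stated: alpha 5%, two-sided unless noted; pre-post correlation r of .4 to .6 (.6 is the SAP's ICC carried back to baseline); 50, 45 or 40 per arm observed at the visit. The last two reflect the 80-90% retention that the protocol's Preliminary/Pilot Studies section reports for the team's earlier studies.

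**1. The SAP's figure.** Design effect = 1 + (2 - 1) x .6 = 1.6; 200/1.6 = 125. Reproduced exactly. At 62.5 per arm and .5 SD, two-sided power is .798 (normal) or .792 (t), so more than .8 is met only within rounding.

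**2. What 125 measures.** The mean of two visits has variance (1 + .6)/2 = .8 per person, and 100/.8 = 125. The mismatch does not depend on the ICC chosen: 200/(1 + ICC) exceeds 100 for every ICC below 1 (133 at .5, 111 at .8).

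**3. The planned contrast.** Take complete data and Time = 0 at the post-intervention visit.
- With treatment-by-time in the model: SE = sqrt(1/50 + 1/50) = .200, effective N = 4/.200² = 100. Generalised least squares gives the same value at ICC 0, .3, .6 and .9.
- Without it: SE = sqrt(.8 x 2/50) = .179, effective N = 4/.032 = 125.

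**4. Unadjusted single-visit power, .5 SD, 50 per arm.** Two-sided: .705 (normal) or .697 (t), with an 80%-power effect of .57 SD (t). One-sided 5%: .804 or .799.

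**5. Adjusted for DV_pre.** Noncentral t with standardised effect .5/sqrt(1 - r²) and 2n - 3 degrees of freedom, two-sided 5%:

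| r | 50 per arm | 45 per arm | 40 per arm |
|---|---|---|---|
| .6 | .87 | .83 | .79 |
| .5 | .82 | .77 | .72 |
| .4 | .77 | .73 | .67 |

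Power of .80 needs r of about .47, .55 and .62 respectively. The mixed model also keeps people seen at only one visit. If 90% or 80% respond independently at each visit, effective n is about 46.5 or 42.5 per arm, and power is .84 or .80 at r = .6 and .78 or .74 at r = .5.

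**6. Drinks per week, single visit, 50 per arm, Wald test on log 1.32 = .278, two-sided 5%.**
- Pure Poisson, intervention rate 4 and control 5.28: SE = sqrt((1/4 + 1/5.28)/50) = .0937, power .84. If 4 is the control rate (intervention 3.03), power is .73.
- A pure Poisson with one common rate has no between-person variance, which contradicts an ICC of .6. A gamma-Poisson at mean 4 with ICC .6 needs 16a/(4 + 16a) = .6, so a = .375 and the variance is 4 + 6 = 10. With intervention rate 4, SE = sqrt((1/4 + 1/5.28 + 2 x .375)/50) = .154 and power is about .44. If the variance is cut by the factor 1 - .6² = .64, power is about .61.

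**The case against.** Four points deserve weight.

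- **Term reduction.** The SAP says, after Equation 1, that Wald statistics will decide which fixed effects are needed. If treatment-by-time were dropped, one constant effect would apply at every visit, with SE .179 and effective N 125, and the SAP's sentence would be coherent. This stands only in part: the Aim 1b section uses the interaction to test H1b, and the Power section does not say that it assumes a constant effect.
- **Sidedness.** H1b is directional and the SAP does not say that the test is two-sided. At one-sided 5%, 50 per arm gives about .80 unadjusted. So the shortfall to .70 depends on a two-sided test. The mismatch between 125 and a single visit does not.
- **Baseline adjustment.** Leaving DV_pre out of the calculation is conservative. If r equals the SAP's own .6, the planned contrast has power .87 with 50 per arm and .83 with 45. The conclusion may well be true although the derivation is not valid. But r and the number observed decide it, and neither is stated.
- **Pilot status.** N was fixed in advance, and a confidence interval will show which effects a null result leaves open. The SAP expects moderate-to-large sleep effects, and even unadjusted two-sided power at 50 per arm is .84 at .6 SD and .98 at .8 SD. This limits the consequence to interpretation.

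On attrition, the SAP does say up to 200 observations, and both documents refer to retention details in a Human Subjects section that is not part of the supplied text. The absence that counts is from the power calculation itself.

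**Conclusion.** The point holds as a mismatch between derivation and contrast. The division giving 125 is correct, but it describes the two-visit average, or a constant effect if treatment-by-time is dropped. For the post-intervention contrast under the planned model, the effective N is 100 with complete data. The sleep claim is therefore unsupported as derived: about .70 rather than more than .8 at two-sided 5% without adjustment, and about .80 at one-sided 5%.

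A reader might infer that the sleep comparison is underpowered or that 150 participants are too few. The documents do not support that. With DV_pre in the model, two-sided power runs from .67 (r = .4, 40 per arm) to .87 (r = .6, 50 per arm), and the documents give neither value.

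A reader might also infer that the drinks-per-week claim is safe because a Poisson calculation gives .84 at 50 per arm. That is not supported either. It requires 4 to be the intervention rate and no between-person variance, whereas overdispersion matching the SAP's ICC gives about .44 unadjusted or .61 with the variance reduction. These last two figures are illustrations under an assumed gamma-Poisson form, not estimates for this trial.

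**What to change.** Change the Power section as follows.

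- **Sleep.** State power for the DV_pre-adjusted single-visit contrast with at most 50 per arm, giving alpha, sidedness, the assumed pre-post correlation and the number expected to be observed. For example: two-sided 5%, r = .6, 45 per arm observed, power .83 for .5 SD and 80% power for .48 SD. The r and the 45 are placeholders that the team must justify. Give .57 SD (two-sided, 50 per arm) as the no-adjustment reference.
- **125.** Keep it only for the effect averaged over both visits, or for a constant effect, and say which. Unadjusted two-sided power for .5 SD is then .79-.80.
- **Drinks per week.** Say which arm has 4 per week, use at most 50 per arm for a single follow-up, and recompute with an overdispersion assumption consistent with the ICC of .6.

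The cost is a few sentences in the SAP, with no added participants or assessments and no change to the design. The downside is that the stated figures may look less favourable, and the team must commit to a correlation, a retention rate and a dispersion value.

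### The stated >.8 power for a 32% difference in drinks per week allows for little or no between-person variance; if the SAP's ICC of .6 applies to drinks, power at one follow-up is about .60 to .65

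*SAP*

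**What the plan says.** All the figures are in the SAP's Power paragraph. The sample size came first and the detectable effects were worked out from it: "We used PASS software to estimate effect sizes based on proposed study sample size for Aim 1b". Each comparison has "2 conditions x 50 subjects per condition x 2 observations per subject", or 200 observations. With "an anticipated intra-class correlation (ICC) among survey responses for the same individual of .6", this becomes an effective sample size of 125.

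The alcohol illustration uses "typical number of drinks per week, which tends to show a count distribution", supposes that "the base-rate were 4 drinks per week", and claims more than .8 "power to detect a 32% increase in the count of drinks per week in the control compared to intervention group". It expresses this as a rate ratio of 1.32 and attaches the claim to each follow-up taken singly. It gives no dispersion or between-person variance for the count, no alpha, and no statement of which arm drinks 4 per week.

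Two other parts of the SAP bear on this. The model description under Statistical Design and Power says that such outcomes "often have skewed distributions that are better represented by the Poisson or Negative Binomial distributions". It specifies a count model that keeps the person-level random effects and the baseline covariate (DV_pre) of Equation 1 and changes only the Level 1 distribution to Poisson. The Aim 1b section makes the difference at post-intervention the primary comparison. It tests that difference through the treatment intercept, alongside treatment-by-time terms.

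**The concern.** A within-person correlation of .6 means that people differ persistently in how much they drink. In a Poisson mixed model that between-person variance adds to the Poisson variance and widens the standard error of the treatment contrast. A detectable ratio of 1.32 with about 100 people and a mean near 4 leaves almost no room for it. The ICC was used to reduce the number of observations, but its effect on the variance of the count does not appear to have been carried through.

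This is the SAP's only power statement for an alcohol outcome, and alcohol use and consequences are central to H1b in the protocol's Specific Aims. The protocol's Open Pilot Trial and Pilot Study text says that the pilot is needed to support a larger trial. Planners of that trial should not rely on a sensitivity to drinking effects that this one does not have.

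**Working it through.** **Inputs.** From the SAP: 50 per arm, two follow-ups, ICC .6, base rate 4, ratio 1.32 (control over intervention), DV_pre in the model. Assumed, because the documents do not say: two-sided alpha .05; 4 is the intervention mean, so control is 4 × 1.32 = 5.28; baseline correlates .6 with follow-up (set equal to the ICC); no dropout. ln 1.32 = 0.2776, and its square is 0.0771. Let φ be the variance-to-mean ratio.

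**Two formulas.**
- Wald test on the log rate ratio: SE = √{φ[1/(50×4) + 1/(50×5.28)]} = √φ × 0.0937; power = Φ(0.2776/SE − 1.96).
- Poisson-regression sample-size formula with equal arms: power = Φ{[√(N×4×0.0771/φ) − 1.96×√4]/√(2 + 2/1.32)}, where √(2 + 2/1.32) = 1.875.

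**Reproducing the SAP's figure (φ = 1, one visit, N = 100).**
- Wald: Φ(0.2776/0.0937 − 1.96) = Φ(1.00) = .84.
- Regression formula: Φ[(5.553 − 3.920)/1.875] = Φ(0.871) = .81. Solved for .8 power, it needs N = (3.920 + 0.842×1.875)²/(4×0.0771) = 98, and at N = 100 its detectable ratio is 1.316, which rounds to 1.32.
- At N = 125 and φ = 1 the detectable ratio would be 1.27 to 1.28.

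So φ = 1 with 50 per arm is the closest match.

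**What an ICC of .6 implies.** In a Poisson random-intercept model the marginal variance is the mean plus τ², and ICC = τ²/(τ² + mean). At mean 4, τ²/(τ² + 4) = .6 gives τ² = 6, total variance 10 and φ = 10/4 = 2.5.
- Adjusted for baseline, one visit: 2.5 × (1 − .6²) = 1.6.
- Mean of two visits, unadjusted: 2.5 × (1 + .6)/2 = 2.0.
- Mean of two visits, adjusted: 2.0 − (.6×2.5)²/2.5 = 2.0 − 0.9 = 1.1.

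**Power for ratio 1.32, 50 per arm.**

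| Contrast | φ | Wald | Regression formula |
|---|---|---|---|
| One visit, pure Poisson | 1.0 | .84 | .81 |
| One visit, baseline-adjusted | 1.6 | .65 | .60 |
| One visit, unadjusted | 2.5 | .47 | .41 |
| Mean of two visits, baseline-adjusted, constant effect | 1.1 | .81 | .77 |

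Simulation of gamma-Poisson data (1,500 trials, robust standard errors) gave .66, .48 and .82 for the last three rows.

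**Ratio detectable with .8 power at one visit.** Wald: 1.39 adjusted, 1.50 unadjusted. Regression formula: 1.41 and 1.54.

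**Sensitivity.**
- Size of the ICC: by Wald, power is .8 when φ = 0.0771/[2.80² × (1/200 + 1/264)] = 1.12. Unadjusted, φ = 1/(1 − ICC), so the limit is an ICC of about .11. Adjusted with baseline correlation equal to the ICC, φ = 1 + ICC, so the limit is about .12. At ICC .3, power is .70 unadjusted and .74 adjusted.
- Using the effective size (62.5 per arm) with φ = 1.6 and 2.5: Wald .74 and .55.
- Reference arm: if 4 is the control mean and intervention is 4/1.32 = 3.03, Wald gives .53 adjusted and .37 unadjusted, and .73 even for pure Poisson. The regression formula hardly moves (.59 and .42).
- Negative binomial variance (quadratic in the mean), Wald: .61 adjusted, .44 unadjusted.
- 20% dropout (the protocol cites 80-90% retention in earlier work), Wald: .55 adjusted, .39 unadjusted.

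**The case against.** A reader might infer that the SAP must have used pure Poisson variance. The documents do not support that: the PASS inputs are not given, and other routes also reach about .8. These are N = 125 with φ of about 1.3 (regression formula) to 1.4 (Wald), or pure Poisson at N = 125 with 4 as the control rate (Wald .82). This stands, and pure Poisson is only the closest match. But none of these routes comes near φ = 2.5.

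A reader might also infer that Poisson variance and an ICC of .6 contradict each other outright. They need not. A shared Poisson component with mean 2.4 plus independent ones with mean 1.6 has mean 4, variance 4 and correlation 2.4/4 = .6. The conflict arises under the SAP's random-effects model, and only if an ICC given for survey responses in general applies to drinks per week. That condition stands too. The ICC need not be exactly .6, however, since power falls below .8 at about .11.

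The strongest defence is that the model uses both follow-ups and that the SAP allows unnecessary terms to be dropped. A baseline-adjusted two-visit average then has about .8 power. This is correct as arithmetic, but it is not the stated claim, which is for any single follow-up. It is also not the primary comparison: with the treatment-by-time term kept, the post-intervention intercept is close to a one-visit test.

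Finally, this is a pilot, its sample was fixed in advance, and the count sentence is a hypothetical illustration. No test or estimate changes. That limits the consequences, but it does not make the stated figure right.

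**Conclusion.** The concern holds in conditional form. The claim of more than .8 power for a ratio of 1.32 at any single follow-up is consistent with little or no overdispersion. If the ICC of .6 applies to drinks per week, the SAP's Poisson mixed model gives variance about 2.5 times the mean. One-visit power with 50 per arm is then about .60 to .65 under the planned baseline-adjusted model. Dropout lowers it, as does 4 being the control rate (clearly by Wald, slightly by the regression formula).

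This rests on two-sided alpha .05, a baseline correlation of .6 and 4 as the intervention mean, none of which the SAP states.

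Two stronger conclusions are tempting. One is that the trial has only an even chance of detecting a 32% difference. That uses the unadjusted .41 to .47, whereas Equation 1 always includes DV_pre. The other is that a null drinking result will be read as ruling out a 32% difference. No section plans such a reading. The supported conclusion is that the power figure is overstated for the contrast it names.

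**What to change.** Recompute the count figure for 50 per arm at one visit. Use a Poisson random-intercept or negative binomial model with DV_pre and between-person variance consistent with the stated ICC. Use one method for both power and detectable ratio. Then either:
- replace 1.32 with a detectable ratio of about 1.4 for the baseline-adjusted one-visit contrast (about 1.5 unadjusted); or
- keep 1.32 and say explicitly that it applies only to the baseline-adjusted average over both follow-ups with a constant effect.

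In either case, state the dispersion, the baseline correlation, alpha and its sidedness, the contrast powered, and which arm has the base rate of 4. If the authors expect a different ICC for drinks than for the other survey measures, they should give it.

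The cost is a change of SAP wording and a less favourable stated effect. No participants, data collection or analysis model need change.
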